#### 6.4.3 Definition of OS and TTP

TTP is defined as the time from enrollment to disease progression. Disease progression will be defined as PD in the target volume, or development of distant disease. OS is defined as the length of time from enrollment to confirmed death from any cause.

#### *6.4.4 QOL evaluation*

QOL evaluation will be carried out according to the treatment schema in section 6.0. The survey will be the FACT-G and will be administered prior to SBRT, after completion of SBRT, and at each follow-up. See appendix A for more details.

#### *6.4.5 Safety evaluation*

All patients will be monitored for potential treatment-related toxicity throughout treatment as detailed in the schema. Toxicity will be graded according to the CTCAE, which is further detailed in section 8.2.1. Acute toxicity is defined as toxicity occurring within 3 months of completion of SBRT. Late toxicity is defined as toxicity occurring greater than 3 months after treatment.

## 7.0 STATISTICAL CONSIDERATIONS

### 7.1 Study Objectives and Design

The primary objective is to determine the LPFS in subjects with resected pancreatic adenocarcinoma with close or positive margins treated with SBRT. Secondary objectives include the evaluation of TTP, OS, acute and late toxicities, and QOL. These study endpoints are defined in Section 6.4.

This clinical trial is planned as a prospective single-arm phase II study. The treatment schema is shown in Section 6.3a.

### 7.2 Sample Size and Accrual Rate

#### 7.2.1 Sample Size

From the Investigators' treatment experience, the 2-year local progression-free survival rate for the standard of care is 40%. This phase II study aims to improve it to 60% with SBRT. We plan to have 24 months of accrual, and 24 months of follow-up beyond the last patient enrolled on study. Under assumption of exponential survival, a total of 50 patients will provide 94% power to detect a statistically significant improvement in survival by one-sided log-rank test at significance level 0.05. Assuming that there will be no loss to follow up and no ineligible case, a total of 50 patients will be accrued for this trial.

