### 1.2 *Radiation therapy as adjuvant treatment in pancreatic adenocarcinoma*

For many years chemoradiation was considered the standard of care after patients underwent resection of pancreatic carcinoma. This was mainly based on a small phase III randomized control trial by the Gastrointestinal Tumor Study Group (GITSG) (2). This trial randomized 43 patients to surgery with or without adjuvant 5-FU based chemoradiation. The radiation was delivered using outdated techniques (AP/PA and in a split course) to a total dose of 40 Gy. The patients in the experimental arm also received 2 years of adjuvant 5-FU. The experimental arm had a median OS of 20 months compared to 11 months in the control arm. Regardless, 50% of patients in both arms still developed local recurrence. There are also two large retrospective series from Johns Hopkins and the Mayo clinic. The JHU series contains over 600 patients, with 44% having received 5-FU based CRT to a median dose of 50 Gy. The other 44% did not receive adjuvant therapy. The CRT group had a median OS of 21.2 months compared to 14.4 months in the observation group (3). The Mayo series had 472 patients, all with an R0 resection. The median RT dose was 50.4 Gy and almost all patients received 5-FU. The median OS again favored CRT with a median OS of 25.2 months compared to 19.2 months in patients who were observed (4).

A few other studies have examined other adjuvant CRT regimens utilizing non-5-FU-based chemotherapy. RTOG 9704 compared gemcitabine to 5-FU before and after 5-FU based CRT. The study included 451 patients with gross total resection. The radiation dose was 50.4 Gy delivered using modern methods. There was a trend towards improved 3 year OS (31% vs. 22%) with the use of gemcitabine. Local recurrence remained a significant source of failure, but was lower compared to older studies at approximately 25%. Distant metastasis remained the most significant site of failure at greater than 70%, highlighting the importance of systemic therapy (5). The ACOSOG also published a small phase II trial of 89 patients with R0/1 resection of pancreatic head adenocarcinoma treated to 50.4 Gy along with chemotherapy. The chemotherapy was relatively intense, consisting of 5-FU, cisplatin, and alpha interferon and 96% of patients had grade 3 toxicity or greater. Despite such intense therapy local recurrence still remained around 50%, but systemic therapy only made up 35% of failures (6).

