### 1.3 *Chemotherapy alone as adjuvant therapy*

There are a few key studies supporting the adjuvant use of chemotherapy alone after resection of pancreatic cancer. ESPAC-1 was a complex 2x2 factorial designed study with over 500 patients. The arms were 5-FU based CRT (split course technique), adjuvant 5-FU/leucovorin alone, both

CRT followed by chemo, or observation. For all patients, chemotherapy improved median survival from 14 months to 19.7 months. For patients that received chemotherapy the 5 year OS was 21% compared to 8%. When analyzing the effect of CRT, it appeared to have a detriment, with a 5 year OS of 10% compared to 20% when chemoradiation was not given. Drawbacks of this study include its complex design, use of outdated radiation techniques, lack of RT quality assurance, and the ability of treating physicians to give “background” therapy (7). The CONKO-001 study randomized 368 patients with a R0/R1 resection to observation of gemcitabine alone for 6 cycles. The use of adjuvant gemcitabine improved disease free survival from 7 months to 14 months, but not OS (22 months vs. 20 months) (8). There was also a metaanalysis published in 2005 examining outcomes of patients in randomized adjuvant trials. This study included 875 patients from 6 trials. The investigators found that chemotherapy improved median OS from 14 months to 19 months. Chemoradiation did not provide a statistically significant benefit (15.2 months to 15.8 months). Of interest, on subgroup analysis it was determined that CRT was more effective for patients with a positive margin resection (9).

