### 6.2 Evaluation during treatment

The subjects will be carefully followed while on active treatment and post-treatment for 24 months, or until death. Evaluation during treatment will consist of the following activities:

- 6.2.1 Administration of SBRT
- 6.2.3 Interim medical history and physical examination at baseline, prior to SBRT treatment, at the end of SBRT, and 10-12 weeks after SBRT then every 3 months thereafter for up to 24 months.
- 6.2.4 Serum chemistry and electrolytes to include BUN, creatinine, sodium, potassium, bicarbonate, chloride, calcium, magnesium, glucose, total bilirubin, AST, ALT, alkaline phosphatase post-treatment as clinically indicated
- 6.2.5 Hematologic studies to include CBC with differential and platelet count prior to SBRT and repeated 10-12 weeks later and then at follow-up as clinically indicated.
- 6.2.6 CT scan will be obtained at 10-12 weeks post-treatment and will be reviewed for evidence of response. Since these subjects will likely have no gross disease on imaging, the main goal of the follow-up scans is to monitor for local and distant progression as defined below.

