### 6.3 Treatment schedule

Parameter	Pre-Study	SBRT			10-12 weeks post-treatment	Q 3 months until 24 months
		Fx 1	Fx 2	Fx3		
History	X	X		X	X	X
Physical exam	X	X		X	X	X
Measurement of disease	X				X	X
Performance Status	X				X	X
Serum Chemistry	X*				X ▲	X ▲
Hematologic Studies including CBC	X*				X	X ▲
CT Scan	X				X	X Ω
Serum or Urine Pregnancy Test for WOCBP	X					
Histologic and Morphologic Confirmation and Margin Status	X					
QOL assessment	X				X	X

\* Within 30 days of study start

▲If clinically indicated

ΩMay be modified by oncology team if patient receives system therapy

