#### 6.4.2. Definition Local Progression Free Survival

In this study, LPFS is defined as the time from enrollment to first documentation of progressive disease (PD) in the target lesion. Death or development of distant disease is not regarded as an event. For patients that undergo surgical resection, local progression will be defined as disease recurrence detected on follow-up imaging (CT or FDG-PET/CT) that is located within the SBRT target volume.

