#### 7.3.3 Analysis of Study Endpoints

Survival (LPFS, OS, TTP) will be estimated by the Kaplan-Meier method for all evaluable patients and the corresponding median survival times (with 95% confidence interval) reported. The 2-year LPFS will also be estimated along with its 95% confidence interval. The effect of variables listed in Section 7.3.2 will be explored with Cox regression models.

For the QOL data analysis, each item of the FACT-G will be individually assessed. The mean and standard deviation of the observed data will be summarized at each collection time and plotted against time, from baseline through the end of patient follow-up. Generalized linear models (such as cumulative logit models) for repeated measures will be used to explore if there are significant changes in HRQOL over time.

Using NCI Common Terminology Criteria for Adverse Events (CTCAE v4.0), the number of patients experiencing adverse events over their course of treatment will be characterized by type of adverse event and grade, by the time of onset in relation to the first day of therapy, and whether the event is clinically significant. Attribution of adverse events to treatment (unrelated, unlikely, possibly, probably, or definitely) will also be summarized for any serious adverse events (SAEs), CTCAE grade 3 or higher. The percentage of patients experiencing SAEs that are considered to be treatment-related (probable or definite) will be determined. The percentage of patients experiencing the acute and late toxicities associated with SBRT (as defined in Section 6.4) will also be estimated along with its 95% confidence interval.

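### The 94% power ignores deaths without local progression, which the LPFS definition censors; at the survival the Background cites, log-rank power is about 74-84%

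*Combined protocol and SAP*

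**What the plan says.** Section 7.2.1 takes a 2-year LPFS of 40% under standard care and 60% as the target. It assumes exponential survival, 24 months of accrual and 24 months of follow-up after the last enrolment, and concludes that "a total of 50 patients will provide 94% power to detect a statistically significant improvement in survival by one-sided log-rank test" at level 0.05. The accrual target is then set with this proviso: "Assuming that there will be no loss to follow up and no ineligible case".

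Section 6.4.2 defines the endpoint as time to progression in the target and adds: "Death or development of distant disease is not regarded as an event". Section 7.3.3 estimates LPFS by Kaplan-Meier. It states that "The 2-year LPFS will also be estimated along with its 95% confidence interval", and it names no hypothesis test for the primary endpoint.

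On follow-up, 6.2 has patients "followed while on active treatment and post-treatment for 24 months, or until death" and the 6.3 table heads its last column "Q 3 months until 24 months". Section 5.3 sets two years as a minimum, 6.4.1 continues CT to the end of the study, and 7.2.1 counts on 24 months after the last enrolment.

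**The concern.** Despite its name, LPFS here is time to local progression with death as censoring. A patient who dies without local progression leaves the risk set and can no longer contribute an event. Log-rank power depends on the number of events, so deaths reduce it in the same way as dropout. The 7.2.1 calculation has no term for them.

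This would matter little in a disease with long survival. Here the cited survival is short relative to the 24-48 months of observation that the calculation needs. In Background section 1.3, on chemotherapy alone, "chemotherapy improved median survival from 14 months to 19.7 months". The longest median cited after resection, in section 1.2, is "a median OS of 25.2 months compared to 19.2 months in patients who were observed", both groups having had R0 resections.

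If the real power is well below 94%, a negative result will be read as stronger evidence against SBRT than it is. Two further gaps make the operating characteristics harder to pin down. The test that sized the trial does not reappear in the analysis section, and the length of follow-up, which drives the event count, is not stated consistently.

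**Working it through.** **Inputs from 7.2.1.** n = 50, one-sided 0.05, exponential times, 24 months of accrual (taken as uniform), 24 months of further follow-up. With one arm, the log-rank test must be the one-sample version against a fixed reference curve.

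- λ0 = -ln(0.4)/24 = 0.03818 per month
- λ1 = -ln(0.6)/24 = 0.02128 per month
- hazard ratio = 0.02128/0.03818 = 0.557

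**Test.** Z = (E - O)/√E, where O is the observed number of local events and E is λ0 times total time at risk. Reject if Z > 1.645.

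**Reproducing the plan's figure (no deaths).** Follow-up T is uniform on 24-48 months, so the average of exp(-λ1T) is (0.60 - 0.36)/(24 × 0.02128) = 0.470. Expected local events are 50 × (1 - 0.470) = 26.5. Simulated power is 94.1% (40,000 trials), so the 94% is correct for its own inputs.

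**Adding deaths.** Assumption: exponential death, independent of local progression, with hazard μ = ln 2/(median OS). Expected local events are 50 × [λ1/(λ1+μ)] × [1 - average of exp(-(λ1+μ)T)]. For median OS 14 months, μ = 0.0495 and λ1+μ = 0.0708. The first factor is 0.301 and the second is 1 - 0.088 = 0.912, so events = 50 × 0.301 × 0.912 = 13.7.

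A hand check on power uses expected E = O/0.557 and Φ[(E - O)/√E - 1.645]. With no deaths, E = 47.6 and Φ(3.05 - 1.645) = 92%. At 14 months, E = 24.6 and Φ(2.19 - 1.645) = 71%. This approximation runs 2-3 points below simulation but shows the same drop.

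Simulated results, 40,000 trials per scenario:

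| Median OS (months) | Dead without local progression by month 24 | Local events, 24-48 months | Power, 24-48 months | Local events, 24-month cap | Power, 24-month cap |
|---|---|---|---|---|---|
| No deaths | 0% | 26.5 | 94% | 20.0 | 88% |
| 14 | 57% | 13.7 | 74% | 12.3 | 71% |
| 20 | 46% | 16.3 | 81% | 14.1 | 76% |
| 25.2 | 39% | 17.8 | 84% | 15.1 | 78% |

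Simulated type I error is about 4% in these scenarios, so the test is slightly conservative.

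**Sensitivity to independence.** Let the death hazard triple after local progression, holding median OS at 14, 20 and 25.2 months. Power is 78%, 84% and 87% with 24-48 months of follow-up, and 74%, 79% and 81% with a 24-month cap.

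**Break-even.** Under independent death and 24-48 months of follow-up, power is 87.3% at a median OS of 36 months, 89.1% at 48, 90.3% at 60 and 92.4% at 120. Even 90% therefore needs about 60 months, more than twice the longest value cited (60/25.2 = 2.4).

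**If the interval in 7.3.3 were used as the test.** The plan does not state this rule. Requiring the two-sided 95% Kaplan-Meier interval at 2 years to exclude 40% would have about 45-60% power with log-log limits and 54-67% with plain limits, over the same survival range.

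**The case against.** The strongest reply is that the size of the shortfall rests on inputs the protocol does not give.

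- **Independence.** If patients tend to die soon after local progression, fewer deaths occur before it and the loss is smaller. A tenfold post-progression hazard gives about 81-90% with 24-48 months of follow-up. Near-immediate death after progression gives 84%, 90% and 92%. This stands as a limit on precision, but no version reaches 94%.
- **Survival inputs.** The 14-month end is a figure without chemotherapy, whereas section 3.5 allows systemic therapy after SBRT. Cited medians of 19-25.2 months in treated patients give about 80-84% under independence. Against that, the 25.2-month series was entirely R0 while this trial enrols positive margins, and the 11-month surgery-only control arm in section 1.2, left out of the range, would give 69%. The range is illustrative in both directions.
- **Wording.** Death is not loss to follow-up in the usual sense, and the no-loss proviso is attached to the accrual number. That is fair: the defect is best described as an omitted allowance. The shortfall is the same either way.
- **Follow-up.** Sections 5.3, 6.4.1 and 7.2.1 can be read together; only 6.2 and 6.3 point to a 24-month stop. That narrows the inconsistency without removing it.
- **Missing test.** Not naming the test in 7.3.3 does not alter the power of the log-rank test. It does leave the success rule open.

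**Conclusion.** The concern holds. The 94% is correct arithmetic for a trial in which nobody dies without local progression, and the endpoint definition together with the cited survival makes that unrealistic. With exponential death independent of local progression and median OS of 14-25.2 months, power is about 74-84% with 24-48 months of follow-up and 71-78% if follow-up stops at 24 months. The chance of missing a true improvement to 60% is then 16-26% on the longer follow-up, against the 6% implied. Tripling the death hazard after progression brings that to 13-22%. Confidence is high that power is below 94%; the exact figure depends on survival and dependence assumptions that the protocol does not supply. The point should be fixed, but it does not invalidate the design.

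**What to change.** 1. **Section 7.2.1.** Keep n = 50 and state power conditionally. It is 94% if no patient dies without local progression. Because such deaths are censored under 6.4.2, it is about 74%, 81% and 84% for median OS of 14, 20 and 25 months with 24-48 months of follow-up, assuming exponential death independent of local progression. If follow-up is fixed at 24 months per patient, the figures are about 71%, 76% and 78%.
2. **Section 7.3.3.** Name the one-sample log-rank test against the exponential curve with 40% at 2 years, one-sided 0.05, as the primary test. Keep the 95% interval for 2-year LPFS as descriptive. A 90% interval beside it, which would match the one-sided level, is optional.
3. **Follow-up.** Reconcile 5.3, 6.2, 6.3, 6.4.1 and 7.2.1, then keep only the power figures that match.

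The cost is wording and a less favourable stated power, with no extra patients. If the sponsor prefers to restore about 94%, a closed-form calculation with 24-48 months of follow-up and independent death puts the need at about 95, 85 and 75 patients for median OS of 14, 20 and 25.2 months. That formula gives 93% at the plan's own inputs.

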#### 7.2.2 Rate of Accrual

We anticipate that 2 to 4 study-eligible patients will be enrolled per month. Thus, our planned study size of 50 patients to be enrolled within 24 months is well within our capacity.

### 7.3. Statistical Analyses

#### 7.3.1. Analysis Set

The data from all evaluable patients will be used in the analyses of survival, safety, tumor response, and health related QOL. Evaluable patients are those meeting all of the protocol inclusion/exclusion criteria and receiving at least one fraction of SBRT.

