## 4.0 SUBJECT SELECTION AND ELIGIBILITY

### 4.1 Selection of subjects

Enrollment is defined as the first day of protocol therapy.

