#### 4.1.3 Exclusion criteria

Subjects meeting any of the following exclusion criteria are not to be enrolled in the study:

- Non-adenocarcinomas, adenosquamous carcinomas, islet cell carcinomas, cystadenomas, cystadenocarcinomas, carcinoid tumors, duodenal carcinomas, distal bile duct, and ampullary carcinomas are not eligible.
- Evidence of distant metastasis on upright chest x-ray (CXR), computed tomography (CT) or other staging studies
- Subjects with recurrent disease

- Prior radiation therapy to the upper abdomen or liver
- .
- Subjects in their reproductive age group should use an effective method of birth control. Subjects who are breast-feeding, or have a positive pregnancy test will be excluded from the study
- Any co-morbidity or condition of sufficient severity to limit full compliance with the protocol per assessment by the investigator
- Concurrent serious infection
- Previous or current malignancies of other histologies within the last 5 years, with the exception of cervical carcinoma in situ, adequately treated basal cell or squamous cell carcinoma of the skin, and treated low-risk prostate cancer.

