#### *7.4. Early Stopping for Toxicity*

Toxicity will be monitored continuously, with protocol amendment being made as needed. For safety, we will consider that regimen to be excessively toxic and stop accrual if, at any time, the observed rate of grade 3-5 acute or late toxicity as defined above in Section 6.4.5  $\geq 33\%$  and at least 4 toxicities have been observed.

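### Section 7.3.1 leaves SBRT-treated patients later found ineligible out of the safety analysis; a safety set of all treated patients is needed

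*Combined protocol and SAP*

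**What the plan says.** Section 7.3.1 (Analysis Set) names a single population for all analyses: "The data from all evaluable patients will be used in the analyses of survival, safety, tumor response, and health related QOL". Membership has two conditions: "Evaluable patients are those meeting all of the protocol inclusion/exclusion criteria and receiving at least one fraction of SBRT". The document defines no separate safety or all-treated set.

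Five other places bear on this:

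- Section 4.1: "Enrollment is defined as the first day of protocol therapy".
- Section 6.4.5: "All patients will be monitored for potential treatment-related toxicity throughout treatment". Section 8.2.1 likewise requires every adverse event to be recorded.
- Section 7.3.3 reports the percentage of patients with acute and late SBRT toxicity, with a 95% confidence interval. Toxicity is a secondary objective (Section 2.0).
- Section 7.2.1 sizes the trial on the words "Assuming that there will be no loss to follow up and no ineligible case".
- Section 7.4 stops accrual "if, at any time, the observed rate of grade 3-5 acute or late toxicity as defined above in Section 6.4.5" is at least 33% and at least four toxicities have been seen. It does not name an analysis set.

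**The concern.** An eligibility condition can be defended for an efficacy estimate. It does not suit a safety estimate, because a patient who was irradiated was exposed whether or not a criterion was later found unmet. Under Section 7.3.1 as written, such a patient leaves both the numerator and the denominator of the toxicity rates.

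The patients removed need not be a random subset. Some criteria plausibly bear on toxicity. Section 4.1.3 excludes "Prior radiation therapy to the upper abdomen or liver", and Section 4.1.2 sets renal and hepatic limits and rules out uncontrolled inflammatory bowel disease. A patient treated despite missing one of these could be at higher risk than the rest.

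What is at stake is the reported toxicity result of a small trial in which few severe events are expected. In the institution's post-operative series (Section 1.3.1), none of 24 patients had grade 3-4 toxicity.

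**Working it through.** **1. Who is removed.** The set requires (a) eligibility and (b) at least one fraction. Enrollment is the first day of protocol therapy, so condition (b) removes almost nobody who is enrolled. Condition (a) does the removing, and those it removes have started SBRT.

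**2. The plan's own figure.** The plan states no toxicity rate or precision to reproduce. The only related figure is the 94% power in Section 7.2.1. With exponential hazards −ln(0.40)/2 = 0.458 and −ln(0.60)/2 = 0.255 per year (ratio 0.557), 24 months of accrual and 24 of follow-up, a simulated one-sample log-rank test with 50 patients (one-sided 0.05) gives 94.2%. The figure reproduces, and this point does not affect it.

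**3. Effect of one exclusion.** N = 50 comes from Section 7.2.1; the event counts are illustrative. Dropping one affected patient changes x/n to (x − 1)/(n − 1). Intervals are exact (Clopper-Pearson) 95%.

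| All treated | One affected patient dropped |
|---|---|
| 4/50 = 8.0% (2.2-19.2) | 3/49 = 6.1% (1.3-16.9) |
| 1/50 = 2.0% (0.1-10.6) | 0/49 = 0% (0-7.3) |

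The first row moves by about two percentage points. In the second row the exclusion decides whether any severe toxicity is reported at all.

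**4. How likely that is.** The documents give no ineligibility rate, so q = 4% or 10% is an assumption (on average 2 or 5 of 50 patients). With toxicity risk p in ineligible patients, P(at least one affected patient dropped) = 1 − (1 − qp)^50.

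- p = 4%, the acute grade 3 rate in the intact-tumour series of Section 1.3.1 (3 of 71), used here as a reference risk:
  - q = 4%: 1 − (1 − 0.0016)^50 = 7.7%
  - q = 10%: 1 − (1 − 0.004)^50 = 18%
- p = 16%, that is, twice an assumed 8%:
  - q = 4%: 1 − (1 − 0.0064)^50 = 27%
  - q = 10%: 1 − (1 − 0.016)^50 = 55%

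**5. Average bias.** The expected rate in all treated patients is (1 − q) × p_eligible + q × p_ineligible. The evaluable set estimates p_eligible.

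- Equal risk: the two are the same, so the bias is nil.
- 8% against 16%, q = 4%: 0.96 × 8 + 0.04 × 16 = 8.3%, against 8.0%.
- 8% against 16%, q = 10%: 0.90 × 8 + 0.10 × 16 = 8.8%, against 8.0%.

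**The case against.** The strongest reply is that the gap may never open. Section 7.2.1 plans for no ineligible case, and Sections 3.1 and 6.1 put history, pathology, margin status, imaging and laboratory checks before treatment. Average bias is then nil or under one percentage point. The 27% and 55% figures need a 16% risk in ineligible patients, well above the institution's own experience. All of this stands, and it limits the size. It does not remove the point: the statement in Section 7.2.1 is a sample-size assumption, and if it were certain the eligibility condition in Section 7.3.1 would be unnecessary.

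A second reply is that no data are lost, because all patients are monitored, all adverse events are recorded and toxicity is reviewed monthly (Section 8.1). This is right about collection. A reader might infer that ineligible patients go unmonitored, and the documents do not support that. But Section 7.3.1 governs what enters the Section 7.3.3 rates, and there these patients are left out.

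A reader might also infer that the exclusion carries into the stopping rule, so that declaring a patient ineligible could undo a stop. Section 7.4 does not invoke the evaluable set, so this is possible but not stated. Nor is Section 7.4 in conflict with the rest of the plan. It leaves its unit, denominator and attribution categories unsaid, but Section 6.4.5, to which it refers, speaks of treatment-related toxicity, and Section 7.3.3 counts patients. What remains is missing detail.

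**Conclusion.** The point holds for the safety analysis. Followed as written, Section 7.3.1 omits SBRT-treated patients later found ineligible from the Section 7.3.3 toxicity rates, and nothing elsewhere in the plan restores them.

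The size is conditional on an ineligibility rate that the documents do not give. With no treated ineligible patient, the two sets coincide. At the assumed 4% or 10% ineligible, an affected patient is dropped with probability of about 8% or 18% at a 4% risk, and the higher figures apply only if ineligible patients carry a much greater risk. The documents do not support a claim that the plan materially understates toxicity on average. The case rests on how much one patient counts when severe events are few, and on how little the correction costs. It should be made.

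**What to change.** In Section 7.3.1, add a safety set of all patients who receive at least one fraction of SBRT, regardless of eligibility, and use it for the toxicity analyses in Section 7.3.3. Keep the evaluable set for the other analyses.

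As a minor clarification, Section 7.4 should say that treated patients are not left out of the stopping rule because of ineligibility. The sponsor should also state the rule's counting unit, denominator and attribution categories, consistent with Sections 6.4.5 and 7.3.3. Those choices belong to the sponsor, and the limits themselves are not in question here.

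The cost is one sentence in Section 7.3.1 and a short addition to Section 7.4. The sample size, significance level and 94% power are unchanged. There are two downsides. Safety and efficacy denominators will differ if anyone proves ineligible, which a footnote can explain. Toxicity follow-up may also be shorter for some of these patients: Section 8.1.1 lists protocol violation as a reason for removal, and Section 8.2.1 then follows events that continue or emerge within 30 days, so later toxicity might not be captured. The report should state the follow-up actually obtained for them.
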